#### Data analysis (Research Question 2)

- Historical Comparator RCA Observed ABRYSVO-exposed GBS counts will be compared against expected GBS counts using sequential hypothesis testing, adjusting for secular trends in GBS in the historical comparator group, if secular trends are observed. The conditional PmaxSPRT will be used to generate the test statistic (i.e., a log-likelihood ratio) which will be measured against a critical value. The critical value will be dynamic over the course of the analysis, as data accrue.
- Concurrent Comparator RCA Observed ABRYSVO-exposed GBS cases will be compared against expected GBS counts using sequential hypothesis testing. The binomial maximized sequential probability ratio testing (BmaxSPRT) will be used to generate the test statistic (i.e., a log-likelihood ratio) which will be measured against a dynamic critical value.
- Data analysis for SCRI design study Case-centered logistic regression will be used for analysis (Fireman, 2009). Incidence rate ratios with 95% CIs (to estimate relative risk) and attributable risk with 95% CIs per 100,000 doses and 100,000 person-years (to estimate absolute risk) will be calculated.

#### Milestones

The anticipated start of data collection (defined as first date of data extraction) is 01 July 2025, and the end of data collection (defined as last date of data extraction) is anticipated to be no later than 28 February 2029. A final study report is planned for no later than 31 January 2030.

# 5. AMENDMENTS AND UPDATES

Version Identifier	Date	Amendment Type (substantial or administrative)	Protocol Section(s) Changed	Summary of Amendment(s)	Reason
3.0	27 May 2025	Substantial	4, 8, 9.2	Research questions and objectives: In the signal evaluation section, revised the risk window described in this objective to include "or 42	This revision was made to address the FDA's comment received on 27 May 2025 and to align with

				days (depending on length of risk window)".	the remainder of the protocol.
		Substantial	4, 9.2.1.2	Study design (Research Question 2): Revised the SCRI analysis primary risk window to 1-42 days after ABRYSVO vaccination, and the secondary risk window to 1-21 days.	This revision was made to address the FDA's comment received on 27 May 2025.
		Administrative	3, 4	Modified the Pfizer investigator/author list.	Change in Pfizer Principal Investigator
2.0	24 April 2025	Substantial	4, 9.2.1.1.1., 9.2.2.1.1.2.	Added the word "seasonal" to the description of the influenza vaccine throughout the protocol for clarity.	This revision was made to address FDA comment #1 on Research Question 2, received on 03 April 2025.
			9.2.2.1.1.2.	For clarity, added the rationale for an eligibility criterion for the historical comparator group, as well as limiting this exclusion to the Janssen vaccine.	This revision was made to address FDA comment #2 on Research Question 2, received on 03 April 2025.
			9.2.1.1., 9.2.3.2.1.1., 9.2.7.1.	Added text related to new risk window of 1–42 days for all RCAs.	This revision was made to address FDA comment #5 on Research Question 2, received on 03 April 2025.
			4, 9.1.3.1.	Added antecedent vaccination to abstract, Table 2, and paragraph text surrounding Table 2.	This revision was made to address FDA comment #1 on Research Questions 1 and 2, received on 03 April 2025.

4, 9.2.1.1.1, 9.2.2.1.1, 9.2.2.1.1.1., 9.2.2.1.1.2.	Modification of vaccine capture end dates for historical comparator RCA to allow for the full 21 days of follow-up (or 42 days for the 42-day risk window analyses) prior to either FDA approval of ABRYSVO for adults 18-59 years (for historical comparator) or most recent available data (for ABRYSVO exposed). This ensures the two groups are comparable in the scenario that GBS events are not evenly distributed throughout the risk window and restricts follow-up for historical comparator to a pre-ABRSVO timeframe.	Additional change
6	The anticipated start of data collection (defined as first date of data extraction) is now 01 July 2025, based on the expected date of SAP finalization.	Additional change
9.2.1.1.	Modified the RCAs to not require adjustment for incomplete data. When we thought about this again, we realized that it would be better to wait the 6-months to obtain data completeness than to wait only 3-months and introduce the assumption that comes with adjustment for incomplete data. The assumption with only waiting 3 months and adjusting is that we have correctly specified the curve of when data comes in and is complete and, if this curve is mis-specified, could bias our results. Dates of delivery of RCAs to the FDA remain unchanged.	Additional change
9.2.2.	Added GBS washout criterion throughout safety studies so that everyone was at risk of	Additional change

	GBS (per our algorithm) on
	day 1 of follow-up. Take, for
	example, the criterion for the
	ABRYSVO-exposed group:
	"No code for GBS or its
	sequalae, in any setting or
	position, in the 365 days prior
	to and including ABRYSVO
	vaccination."

#### 6. MILESTONES

Below is the anticipated schedule of milestones, based on the anticipated data lags and timing of data availability for the planned data sources.

Milestone	Planned Dates
Registration in the HMA-EMA Catalogues of RWD studies	Prior to start of data collection
Start of data collection 	01 July 2025
End of data collection 	28 February 2029
GBS Epidemiology and Natural History Final Report (Research Question 1)	30 September 2026
RCA Report 1 (2024/2025 and 2025/2026 RSV seasons) 	30 September 2027
RCA Report 2 (2026/2027 RSV season)	30 September 2028
RCA Report 3 (2027/2028 RSV season)	30 September 2029
Final study report (will include SCRI analysis  )	31 January 2030

 Estimated date for when data are extracted for first GBS Epidemiology and Natural History report. Start of data collection will occur after submission of final protocol and SAP finalization, which may be adjusted should there be any further feedback from the FDA.

#### 7. RATIONALE AND BACKGROUND

ABRYSVOTM is a bivalent, adjuvanted RSVpreF vaccine that was approved in the US on 31 May 2023 for the prevention of RSV-LRTD in people ≥60 years of age, and on 21 August 2023 for the prevention of RSV-LRTD in infants from birth up to 6 months of age by immunization of pregnant individuals at 32 through 36 weeks gestational age of pregnancy. Pfizer is currently conducting multiple PASS in the US to evaluate the risk of GBS among individuals aged ≥60 years of age who are vaccinated with ABRYSVO (Studies C3671031 and C3671054) and among pregnant individuals who are vaccinated with ABRYSVO (Studies C3671026, C3671027, C3671041, C3671042). The US FDA approved ABRYSVO use in adults 18-59 years of age at increased risk of RSV-LRTD on 22 October 2024; recommendations from the Advisory Committee on Immunization Practices (ACIP) on use in this age group are pending as of January 2025.

 Reflects final dataset extracted for analysis (includes data lag time and potential medical chart review).

 RCA reports will provide a high-level summary of cumulative safety monitoring results.

 The SCRI analysis may be triggered at an earlier date due to a statistically significant finding in the RCA. In this scenario, the final study report with the SCRI analysis and chart-confirmed GBS cases will be delivered to the FDA approximately 12 months, dependent on chart retrieval, after the statistically significant finding from the RCA is reported.

The epidemiology of GBS may be changing, with evidence of increasing prevalence globally. In North America, a 41.2% increase in the age-standardized prevalence of GBS per 100,000 population was observed between 1990 and 2019. Causes for the change are unknown but may be due to factors including increasing rates of infections and better surveillance for GBS. While many have published on the epidemiology of GBS,  important questions remain unanswered. For example, there is concern that long-term sequelae from COVID-19 may impact GBS risk and, thus, may have changed the distribution of preceding risk factors.  Further, the background incidence rate of GBS has been reported in recent years,  but not for important subgroups, such as those with certain underlying conditions. A better understanding of the epidemiology of GBS in the US, including preceding risk factors and contemporaneous background rates, is important to contextualize the risk of GBS after vaccinations and can inform vaccine safety studies of GBS risk.

This protocol complements ABRYSVO's clinical development program, which observed no GBS events among ABRYSVO-vaccinated adults 18-59 years of age. This is a PASS to monitor the incidence of GBS in ABRYVSO-vaccinated adults 18-59 years of age at increased risk of RSV-LRTD. This protocol additionally complements Studies C3671031 and C3671054 with analyses of the epidemiology and natural history of GBS in the US.

This noninterventional study is designated as a PASS and is a commitment to the US FDA as a postmarketing requirement (PMR).

#### 8. RESEARCH QUESTION AND OBJECTIVES

This study has 2 research questions, each with multiple objectives.

**Research Question 1:** What is the epidemiology and natural history of GBS in the US for adults  $\geq$ 18 years of age between 2017 and 2024?

#### GBS epidemiology and incidence

#### Objectives:

- Estimate the incidence of GBS overall and in subgroups of interest (e.g., age, sex, comorbidities, region) over time.
- Describe individuals with GBS with respect to demographics, clinical characteristics, risk factors, treatment, and outcomes.

#### GBS etiology

#### Objectives:

• Conduct a detailed medical record review of a sample of GBS cases to validate a claims-based algorithm and to identify potential causes of GBS.

• Perform an exploratory data mining-based signal detection analysis to identify specific vaccines, drugs, and infections potentially associated with GBS.

**Research Question 2:** What is the risk of GBS after exposure to ABRYSVO among non-pregnant recipients 18-59 years of age at increased risk of RSV-LRTD?

#### Objectives:

- Signal Detection: Among non-pregnant individuals 18-59 years at increased risk of RSV-LRTD, compare observed GBS case counts after ABRYSVO vaccination against expected GBS case counts via RCA.
- Signal Evaluation: Among non-pregnant individuals 18-59 years of age, assess risk of GBS in the 21 days or 42 days (depending on length of risk window) following ABRYSVO vaccination using a SCRI design.

#### 9. RESEARCH METHODS

#### 9.1. Research Methods for Research Question 1

Research Question 1: What is the epidemiology and natural history of GBS in the US for adults ≥18 years of age between 2017 and 2024?

# GBS epidemiology and incidence

#### Objectives:

- Estimate the incidence of GBS overall and in subgroups of interest (e.g., age, sex, comorbidities, region) over time.
- Describe individuals with GBS with respect to demographics, clinical characteristics, risk factors, treatment, and outcomes.
- GBS etiology
- Objectives:
- Conduct a detailed medical record review of a sample of GBS cases to validate a claims-based algorithm and to identify potential causes of GBS.
- Perform an exploratory data mining-based signal detection analysis to identify specific vaccines, drugs, and infections potentially associated with GBS.

#### 9.1.1. Study Design for Research Question 1

# 9.1.1.1. Study Design for GBS epidemiology and incidence

To understand the epidemiology of GBS in the US in recent years, descriptive analyses of incident, hospitalized GBS cases will be conducted. Cases will be identified in closed

administrative claims data, or equivalent (i.e., billed diagnosis codes in EHR data), from 2017 through 2024, among adults 18 years and older. This timeframe is restricted to the ICD-10-CM diagnosis code era, removing any potential variability across ICD revisions.

Incidence rates of GBS will be estimated overall and among subgroups of interest. Incidence will be calculated by age group, sex, presence of underlying conditions or events that increase risk of RSV-LRTD, and evidence of certain antecedent infections (e.g., respiratory and gastrointestinal infections, including COVID-19), amongst other characteristics. Incidence rates will be calculated annually for the study period to assess whether the risk of GBS has changed for certain populations, such as those who received a vaccine, had evidence of certain infections, or had certain underlying conditions of interest. Incidence of GBS will also be reported by broad factors, including geographic region and season.

Among the cohort identified with GBS, demographic and clinical characteristics will be summarized, including age, sex, underlying conditions (e.g., chronic conditions, evidence of concurrent pregnancy), and antecedent health events that are potential risk factors for GBS (e.g., infections). Patterns in care and treatment received, as well as outcomes such as length of hospitalization, subsequent healthcare utilization, sequelae of GBS, and death will also be assessed.

# 9.1.1.2. Study Design for GBS etiology: Medical record review

The ICD-10-CM diagnosis code for GBS, G61.0, has been used to identify potential GBS cases in numerous vaccine safety studies, and medical record review has often been performed to adjudicate the diagnosis. Medical record review of cases with G61.0 in the inpatient setting, in the primary position, has yielded PPVs of 79.5% (95% CI 67.6-91.5%),  78.6% (95% CI 63.4-93.8%),  and 71.2% (95% CI 63.5-78.9%)  for Medicare beneficiaries. Other studies have reported a range of PPVs for GBS, from 24% to 82%, with differences in algorithm, ICD-CM revision era, age, and whether the study was for vaccine safety versus descriptive epidemiology  It is not clear whether the PPV for the GBS diagnosis code varies by important characteristics, such as underlying conditions or antecedent events associated with GBS (e.g., vaccination versus infection). Given that PPVs are impacted by the prevalence of the condition under study,  it is important to assess whether the ICD-10-CM diagnosis code for GBS is reliable in identifying true GBS in different populations. Further, PPVs are often utilized for adjustment in vaccine safety studies, such as the SCRI study described in Section 9.2.

This study will validate incident, inpatient GBS diagnosis via ICD-10-CM in the primary position among adults 18 and older (see Table 1 for the algorithm details). A detailed medical record review will be performed for approximately 300 cases in total, sampled based on factors such as age, antecedent vaccination of any kind, certain risk factors (e.g., those associated with RSV-LRTD, recent infection), and calendar time. See Section 9.1.2 for details on sampling for the medical record review.

Abstraction and adjudication forms, as well as standard operating procedures (SOP), will be developed prior to conduct of the medical record review. The medical records from the applicable inpatient encounter and the first post-discharge ambulatory encounter with a

neurologist will be reviewed. If no appointment with a neurologist occurs within approximately 60 days, the first ambulatory encounter post hospitalization will be included in the review. Trained abstractors, or the adjudicators themselves, at each participating RP will extract information from the applicable inpatient and ambulatory records into a structured form or database equivalent (e.g., REDCap). Information will be collected from medical record elements / sections including admission notes, discharge summaries, laboratory test results, radiographic reports, specialist consultation notes, progress notes, and applicable treatments administered. The abstracted information and corresponding records will be reviewed by a clinician, preferably a neurologist, within each RP who will use the study's case definitions for GBS to adjudicate whether a case is confirmed, possible, or not GBS. 1,2 If a neurologist is unavailable, an alternative clinician will conduct the adjudication; training in the adjudication of GBS by a neurologist will be provided if possible. Adjudicators will be asked to assess what they think the cause of GBS was (e.g., infection, vaccination) based on the available information. The database used for abstraction and adjudication will be maintained by each RP and only deidentified data (e.g., relativized dates) will be shared with the Harvard Pilgrim Health Care Institute (HPHCI) for analysis. Aggregate data will be shared externally, including with Pfizer and FDA.

The PPVs and corresponding 95% confidence intervals of the GBS algorithm will be calculated overall and within subgroups for confirmed cases only, and for confirmed and possible cases combined.

Descriptive information will be summarized for diagnoses and care received during hospitalization. The potential cause of GBS, pre-existing conditions, and preceding events will also be summarized for confirmed and possible cases. Where records from preceding ambulatory care are available, information on diagnostic testing and results for antecedent infection, for example, will be reported.

#### 9.1.1.3. Study Design for GBS etiology: Exploratory data mining-based signal detection

[figure not shown]
The study design and research approach for this objective was taken largely from Maro et al., with adaptations. This signal detection analysis will use tree-based scan statistics to broadly search for vaccines, drugs, and infections that may be potential risk factors for GBS.

The method was originally designed and used to detect the association between a specific product (drug or vaccine) and a broad, unspecified range of health outcomes organized in a hierarchical "tree" structure based on their diagnosis codes. For a medical product of interest—influenza vaccine, for example—vaccinees' diagnoses recorded during *post-vaccination* follow-up time are scanned to look for statistically unusual clustering of diagnoses. This method has been used for drugs as well as vaccines.

In this project's application of the method, the analysis will be anchored on the outcome of interest (i.e., GBS) and the software will scan for statistically significant clusters of exposures (i.e., infection diagnoses, vaccines, and drugs) in a pre-specified number of days (e.g., 84) *prior* to the occurrence of the outcome. The hierarchical organization of exposures enables detection of, not only product-specific effects, but also class- or type-wide effects (e.g., mRNA vaccines).

A case-crossover design, which minimizes bias by automatically adjusting for time-invariant confounding, will be implemented (see Figure 1). First, incident cases of GBS will be identified using the ICD-10-CM diagnosis code based algorithm, as described in the below Table 1. Incident exposures (i.e., infection diagnoses, vaccines, and drugs) in the exposure assessment window (to be defined in the SAP) preceding each GBS case will then be identified. Exposures and GBS will not be permitted on the same day because of the inability to distinguish the sequence of events within the same day in administrative claims data. The time-to-event from the exposure to the GBS diagnosis date will be identified. The analysis assesses when a greater than expected frequency of precipitating events occurs that puts the GBS outcome in the risk window. Log-likelihood ratios and Monte Carlo hypothesis testing are used to scan the tree for a potential signal. Further details on this data mining technique are in Section 9.1.7.3.

Figure 1. Example design diagram for the self-controlled case crossover design for GBS.

#### 9.1.2. Setting for Research Question 1

GBS will be identified, for all objectives in this protocol, using an algorithm based on Goud and colleagues (2021), which is very similar to other algorithms.  GBS will be defined as incident primary GBS diagnosis (G61.0) in the inpatient setting, or incident GBS in any setting and any position, with a hospitalization within 7 days where GBS is the primary diagnosis. Incidence is defined using 365-day washout for G61.0 or G65.0 in any care setting.

Table 1. Algorithm for incident GBS

ICD-10-CM code	Setting of code	Definition of "incident"	Performance
G61.0 (Guillain- Barré syndrome)	1) G61.0 as primary hospital discharge diagnosis or 2) G61.0 in any position, any setting, followed by a hospitalization within the 7 subsequent days	No evidence of GBS (G61.0 [GBS] or G65.0 [Sequelae of GBS], any setting, any position) in the 365 days	PPV from study using Medicare data: 79%

for which G61.0 was the primary hospital discharge diagnosis.	prior to the first diagnosis code of interest.	(95% CI, 64% - 94%) 
The date of GBS onset will be considered the date of the first eligible G61.0 code in any setting.		

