#### Setting (Research Question 1)

- GBS epidemiology and incidence The source population will be members of multiple large national health plans; members from 1 or more regional integrated delivery systems or other data sources may also be included. Individuals will meet eligibility criteria if they are ≥18 years of age with ≥365 days of medical and pharmacy coverage preceding cohort entry between 2017 and 2024.
- GBS etiology: Medical record review The source population will be health plan members from regional integrated delivery systems with linked electronic health records (EHR) and administrative billing data. Individuals will meet eligibility criteria if they are ≥18 years of age with ≥365 days of medical and pharmacy coverage preceding cohort entry. Inpatient GBS diagnoses in the primary position will be identified via billed ICD-10-CM diagnosis codes in 2017 through 2024. Medical record review will be primarily conducted via direct access to the EHR, but charts may be requested as needed. To ensure the subgroups of interest (e.g., adults 18-59 years of age at increased risk of RSV-LRTD; adults with recent vaccination) are included in the medical record review, stratified random sampling of eligible cases identified in the billing data will be conducted, though oversampling of more recent GBS diagnoses may be needed.
- GBS etiology: Exploratory data mining-based signal detection The source population will be health plan members. Individuals will meet eligibility criteria if they are ≥18 years of age with ≥365 days of medical and pharmacy coverage preceding date of the incident GBS diagnosis between 2017 and 2024.

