# 9.1.3.3. Variables for GBS etiology: Exploratory data mining-based signal detection

# 9.1.3.3.1. Exposure for GBS etiology: Exploratory data mining-based signal detection

One exposure tree will be developed with top-level categories of vaccines, drugs, and infections. This tree, with hierarchal branches, will allow for the detection of potential associations with GBS on both a specific and group level.

Individuals will be permitted to have multiple exposures if the exposure incidence criteria are met. Rules to define an incident exposure will be included in the SAP. If an individual receives multiple exposures within the same branch of the tree on the same day, then only one of those exposures will be included in the analysis. In this situation, the exposure with the smallest count of unique users over the study period will be retained to increase numbers for the rarer exposures.

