#### 9.1.7.3.1. Data mining analyses and statistical methods

TreeScanTM software (www.treescan.org) will be used to analyze data via a self-controlled case-crossover design. In brief, the tree-based scan statistics use log-likelihood ratio tests to detect elevated frequencies of codes in electronic health data that have been grouped into a hierarchical tree structure and automatically adjusts for multiple overlapping scenarios inherent to data mining. The test statistic is computed via Monte Carlo hypothesis testing. Under the alternative hypothesis, there is at least 1 exposure, or group of exposures, for which there is a temporal cluster of GBS cases during some time interval in the observation window.

The important analytic information in the self-controlled case-crossover design using TreeScan is the time from the exposure to the outcome, within the prespecified observation window. The observation window for analysis (e.g., 84 days) is divided into a risk window and a comparison window. Both "fixed risk window" and "varying risk window" approaches are possible. In a fixed risk window analysis using TreeScan, these values are defined *a* 

priori (e.g., days -21 through -1 prior to GBS diagnosis as the risk window; days -84 through -43 as the comparison window). In a varying risk window analysis, the risk window is allowed to move within the overall observation window, while the comparison window varies accordingly and consists of all the days that are not in the risk window being evaluated. Exposure and GBS will not be permitted on the same day (day 0) because of the inability to distinguish the sequence of events within the same day in administrative claims data.

The self-controlled case-crossover design is compatible with the following 4 tree-based scan statistics: conditional and unconditional Bernoulli tree-based scan statistics for fixed risk window analyses, and conditional and unconditional tree-temporal analyses for varying risk window analyses. The specific statistic(s) that will be used will be specified in the final SAP.

Analyses will be performed with a threshold for statistical significance of p = 0.05 (1-sided).

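### The data-mining scan sets no last exposure date, so for products first used within 2017-2024 the null lag distribution is tilted modestly toward short exposure-to-GBS lags

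*Protocol*

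**What the plan says.** Protocol 9.1.1.3 starts from incident GBS cases and looks back a pre-specified number of days, with 84 as the example; exposures "in the exposure assessment window (to be defined in the SAP) preceding each GBS case will then be identified". Cases qualify by diagnosis date: the abstract's Setting paragraph requires at least 365 days of "coverage preceding date of the incident GBS diagnosis between 2017 and 2024", and 9.1.2.3 gives the same January 2017 to December 2024 period. Section 9.1.2.3 has no criterion on exposure date and states that there are no exclusion criteria.

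Section 9.1.7.3.1 names the analysed quantity as "the time from the exposure to the outcome, within the prespecified observation window". Its fixed-window example is "days -21 through -1 prior to GBS diagnosis as the risk window; days -84 through -43 as the comparison window". The threshold is one-sided p = 0.05.

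Deferred to the SAP are the exposure assessment window, the scan statistic, the choice of fixed or varying risk window, and incident-exposure rules ("Rules to define an incident exposure will be included in the SAP", 9.1.3.3.1). Section 7 records that ABRYSVO was "approved in the US on 31 May 2023 for the prevention of RSV-LRTD in people" aged 60 or over.

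**The concern.** The scan asks whether the exposure-to-GBS lag clusters within the observation window. With no effect, lags should fall in the risk and comparison windows in proportion to window length. Ending case accrual on 31 December 2024 disturbs this: an exposure on 1 December 2024 can be followed by a counted case only at lags of 30 days or less.

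For a product in use throughout, this is offset at the other end. Cases in early 2017 look back into late 2016, and those exposures can appear only at long lags. A product launched inside the period has no 2016 exposures, so nothing replaces the missing long lags.

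The tilt runs in one direction, toward falsely implicating new vaccines, including the sponsor's own. It arises with a constant GBS hazard, so it is distinct from the seasonality limitation in 9.1.9.3.

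**Working it through.** The protocol states no power or error figure for the scan, so there is none to reproduce.

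**Inputs from the protocol:** cases from 1 January 2017 to 31 December 2024 (2,922 days); observation window 84 days; risk lags 1-21, comparison lags 43-84 (21:42, null risk share 1/3); first availability 31 May 2023, which is 581 days counted to 31 December 2024 inclusive.

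**Assumptions:** constant GBS hazard, no true effect, uptake patterns as given below.

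**Last exposure date that can reach every lag:** 31 December 2024 minus 84 days = 8 October 2024.

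**Method.** The expected count at lag L is proportional to g(L), the share of doses given at least L days before 31 December 2024. The null ratio R is mean g over lags 1-21 divided by mean g over lags 43-84. The risk-window share is then R/(R + 2).

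1. *Stable exposure, with look-back into late 2016:* R = 1.000.
2. *New product, uniform uptake from 31 May 2023:* g(L) = (581 − L)/581. The mean lags are 11 and 63.5, so R = (570/581)/(517.5/581) = 0.981/0.891 = 1.10.
3. *New product with share w of its doses in the 2024 season:* g(L) = (1 − w) + w × P(days from dose to 31 December ≥ L).
   - Low end, w = 0.3, doses even from 15 August to 15 November: short lags 1.000; long lags 0.7 + 0.3 × 0.810 = 0.943; R = 1.06.
   - High end, w = 0.5, doses even from 1 September to 31 December: short lags 0.5 + 0.5 × 111/122 = 0.955; long lags 0.5 + 0.5 × 58.5/122 = 0.740; R = 1.29.
   - Two-season patterns for a product launched on 31 May 2023, with 30%-60% of doses in the 2024 season and 16%-30% of all doses in the last 84 days, give R = 1.11-1.23.
4. *All doses in the 2024 season (w = 1), same date ranges:* R = 1.23-1.90.

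**False-positive rate for one node** (exact binomial, null share 1/3):

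| R | Risk share | n = 30, 0.05 | n = 30, 0.001 | n = 120, 0.05 | n = 120, 0.001 |
|---|---|---|---|---|---|
| 1.00 | 0.333 | 4.4% | 0.07% | 3.5% | 0.09% |
| 1.06 | 0.346 | 6.0% | 0.13% | 6.5% | 0.25% |
| 1.10 | 0.355 | 7.3% | 0.17% | 9.4% | 0.45% |
| 1.29 | 0.392 | 15.3% | 0.65% | 32.2% | 4.0% |

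The 0.001 level is only a stand-in for the tree-wide adjustment.

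**After the cut-off.** With exposures ending on 8 October 2024, R is 1.000 for uniform uptake and for the seasonal pattern tested (50% of doses in the 2023 season, 40% in the 2024 season, 10% outside both).

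**The case against.** The strongest reply is that the exposure window and incident-exposure rules are left to the SAP, which could contain a calendar cut-off. It is true that the protocol does not rule one out. But the deferred items read most naturally as the look-back length and the definition of a new exposure, and neither removes the truncation. That comes from accrual by diagnosis date, which the protocol fixes. Choosing a conditional statistic would not by itself remove a tilt specific to one product.

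The second reply is that every case has a full look-back, so the early end of vaccine capture in the historical comparator analysis (9.2.1.1.1) is no precedent. That analysis is anchored on vaccination and this one on the case, so the two are not inconsistent. A full look-back protects stable exposures only.

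The third reply stands in large part: consequences are limited. Section 9.1.9.3 calls the scan hypothesis generating. Section 9.1.7.3.2 allows signals to be set aside for obvious temporal confounding and requires separate controlled studies before any causal reading. Still, a short-lag excess for a new vaccine would not look like obvious confounding.

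A reader might infer that RSV vaccines will show a spurious cluster. The documents do not support that. Ratios of 1.23-1.90 need first use in the 2024 season, whereas ABRYSVO was available from May 2023. For ages 18-59, approved on 22 October 2024, 9.2.1.1.1 expects claims only after an ACIP recommendation still pending in January 2025, so few such doses should be present.

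**Conclusion.** The point holds as a modest, one-directional tilt in the null for products first used inside the period. Exposures in stable use are unaffected. For RSV vaccines a plausible null ratio is about 1.06-1.29. With 30 exposures and a nominal one-sided 5% test, the single-node false-positive rate goes from about 4% to about 7% at a ratio of 1.10 and about 15% at 1.29. After multiplicity control a false signal would be uncommon: at 0.001, about 0.2%-0.7% over those ratios with 30 exposures, and up to about 4% with 120.

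These figures rest on a constant GBS hazard, the example windows in 9.1.7.3.1 and assumed uptake. Severity is low to moderate because the scan is exploratory.

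**What to change.** In 9.1.1.3 and 9.1.2.3, include only exposures dated from 1 January 2017 through the end of case accrual minus the observation window (8 October 2024 for 84 days). Both limits are needed. Dropping late-2024 exposures while keeping those from late 2016, which can appear only at long lags, would tilt stable exposures the other way.

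At minimum, pre-specify this restricted scan as a check that any signal for a product introduced, or rising in use, during the period must survive.

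The cost is one eligibility sentence and about 3% of exposure calendar time (84/2,922). For autumn products it is larger: under the assumed patterns the cut-off removes 41% (38/93 days) to 69% (84/122 days) of 2024-season doses, or roughly 20%-34% of all exposures to a product with half its doses in that season. Running the restriction as a pre-specified check avoids this loss in the main scan.
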